### 11.4 Expedited Reporting by Investigators

The following types of events must be reported by the Investigator in the eCRF within 24 hours of awareness:

- SAEs (See Section 11.1.2 for definition) occurring at any time from the signing of the ICF through the 30-day follow-up period after the last dose of study drug must be reported as SAEs on the eCRF and followed until resolution (with autopsy report if

*CONFIDENTIAL*

applicable). Adverse events classified by the treating Investigator as “serious” require expeditious handling and reporting to the Innovations Safety Department in order to comply with regulatory requirements. Determination of “life-threatening” or “serious” is based on the opinion of either the Sponsor or the Investigator. Additionally, any SAE brought to the attention of an Investigator at any time outside of the time period specified above must be reported immediately to the Sponsor if the event is considered to be drug related.

- All potential ILD/pneumonitis cases should be reported within 24 hours: including both serious and non-serious potential ILD cases (potential ILD is described by the Event Adjudication Site Manual).
- Hepatic events (both serious and non-serious, and clinical laboratory result) which meet the potential Hy’s Law criteria defined as an elevated [ALT or AST]  $\geq 3 \times$  ULN and an elevated total bilirubin  $> 2 \times$  ULN that may occur simultaneously or at different time points during the study, regardless of whether these hepatic events are symptomatic, lead to study drug discontinuation, dose reduction or dose interruption, require corrective treatment, constitute an AE in the Investigator’s clinical judgment. A targeted questionnaire is built within the eCRF to collect relevant additional information for these potential cases. For broad surveillance of hepatotoxicity, hepatic events that meet the biochemical criteria (AST or ALT  $\geq 3 \times$  ULN, TBL  $> 2 \times$  ULN) are included for enhanced data collection.
- Overdose is always serious. By definition an overdose is medically important, which meets the seriousness criterion of important medical event. An overdose can occur with or without an AE. AEs can either be serious or non-serious. Details of the overdose including DS-6157a dosage, clinical course, associated AEs, and outcome must be captured in the narrative form of the eCRF.

All events (serious and non-serious) must be reported with Investigator’s assessment of the event’s seriousness, severity, and causality to the study drug. A detailed narrative summarizing the course of the event, including its evaluation, treatment, and outcome must be provided. Specific or estimated dates of event onset, treatment, and resolution must be included when available. Medical history, concomitant medications, and laboratory data that are relevant to the event must also be summarized in the narrative. For fatal events, the narrative must state whether an autopsy was or will be performed, and include the results if available. Source documents (including medical reports) will be retained at the study site and will not be submitted to the Sponsor for SAE reporting purposes.

Urgent safety queries must be followed up and addressed promptly. Follow-up information and response to non-urgent safety queries must be combined for reporting to provide the most complete data possible within each follow-up.

In the event that eCRF is unavailable, report SAEs on a Serious Adverse Event Report (SAVER) form. All completed SAVER forms must be signed by the Investigator, and e-mailed to the sponsor and CRO using the following contact information (during both business and non-business hours):

*CONFIDENTIAL*

Study Drug: DS-6157a

Sponsor/Innovations Study Numbers: DS6157-A-U101/GI 289

Final Protocol: 17 August 2021 Version 6.0

**11.4.1 Investigator Reporting After Study Discontinuation**

During the 30 days after completing protocol-specific treatment or study discontinuation, treatment-related AEs, SAEs, or deaths determined by the Investigator as treatment-related are to be reported directly to the Sponsor or Innovations Safety.

**11.5 Abnormal Laboratory Values**

All clinical laboratory results, vital signs, and ECG results or findings must be appraised by the Investigator to determine their clinical significance. If an abnormal laboratory value or vital sign is associated with clinical signs and/or symptoms, the sign or symptom should be reported as an AE or SAE, and the associated laboratory value or vital sign should be considered additional information that must be collected on the relevant eCRF screen. If the laboratory abnormality is a sign of a disease or syndrome, only the diagnosis needs to be recorded on the eCRF screen.

Abnormal laboratory values will be reported as an AE if the laboratory result requires an adjustment in the study drug(s) or discontinuation of treatment; and/or laboratory findings require additional testing or surgical intervention; a laboratory result or finding is associated with accompanying symptoms; or a laboratory result is considered to be an AE by the Investigator.

**11.6 Deaths**

Deaths that occur during the protocol-specified AE reporting period that are attributed by the Investigator solely to progression of disease will be recorded on the “End of Study” eCRF screen. However, when a patient dies from disease progression with no other immediate cause, disease progression will be recorded on the eCRF as AE term “disease progression” as well as the outcome, and serious criteria of death, and expeditiously reported to the Innovations Safety Department. All other on-study deaths, regardless of attribution, will be recorded on the eCRF screen and expeditiously reported to the Innovations Safety Department.

When recording a SAE with an outcome of death, the event or condition that caused or contributed to the fatal outcome should be recorded as the single medical concept on the eCRF screen. If the cause of death is unknown and cannot be ascertained at the time of reporting, record “Death” on the eCRF. During post-treatment follow-up, deaths attributed to progression of disease will be recorded on the “Follow-up Summary” and “Death Page” eCRFs.

*CONFIDENTIAL*

### **11.7 Pre-Existing Medical Conditions**

A pre-existing medical condition is one that is present at the start of the study. Such conditions should be recorded on the General Medical History of the eCRF screen. A pre-existing medical condition should be recorded as an AE or SAE only if the frequency, severity, or character of the condition worsens during the study. When recording such events on the eCRF screen, it is important to convey the concept that the pre-existing condition has changed by including applicable descriptors.

### **11.8 New Cancers**

The development of a new primary cancer should be regarded as an AE and will generally meet at least one of the seriousness criteria (see Section 11.1.2). New primary cancers are those that are not the primary reason for the administration of the study treatment and have developed after the inclusion of the patient into the study. They do not include metastases of the original cancer. Symptoms of metastasis or the metastasis itself should not be reported as an AE/SAE, as they are considered to be disease progression.

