### 5.1.2 Dose-Limiting Toxicity

Toxicity will be assessed using the NCI [CTCAE Version 5.0](#).

A DLT is defined as any TEAE that occurs during the DLT evaluation period (21 days starting from Cycle 1 Day 1), excluding toxicities clearly related to disease progression or intercurrent illness, that are Grade  $\geq 3$  according to the NCI [CTCAE Version 5.0](#), with the exceptions defined below.

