## 7. STUDY ASSESSMENTS AND EVALUATIONS

### 7.1 Overview

All patients should visit the study center on the days specified within this protocol. The complete Schedule of Assessments for this study is presented at the beginning of this protocol (see [Assessment Schedule](#)). The key procedures required in this study include:

- All AEs regardless of seriousness or relationship to DS-6157a treatment (called study treatment) spanning from the signing of the ICF until at least 30 calendar days after the patient's last dose of study drug, or the patient's start of another cancer treatment are to be recorded on the corresponding screen(s) included in the eCRF.
- PK samples throughout the study
- Baseline and on-treatment blood biomarker and immunogenicity assessments
- Tumor biopsy biomarker assessments
- Tumor assessments (based on computed tomography [CT]/positron emission tomography [PET]/ and/or magnetic resonance imaging [MRI] scan) according to RECIST Version 1.1 ([Appendix B](#)).

A cycle of treatment is scheduled to last 3 weeks (21 calendar days). Multiple procedures may be scheduled at the same time point relative to DS-6157a dosing. Priority must be given to PK collection at the time specified. Vital signs and ECG assessments must be performed prior to PK sample collections when these assessments are scheduled for the same timepoints.

*CONFIDENTIAL*

Study Drug: DS-6157a

Sponsor/Innovations Study Numbers: DS6157-A-U101/GI 289

Final Protocol: 17 August 2021 Version 6.0

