## **11.2 Recording and Reporting of Adverse Events**

### **11.2.1 Recording of Adverse Events**

All AEs, SAEs, and AESIs will be reported in the eCRF.

All events (serious and non-serious) must be reported with Investigator’s assessment of the event’s seriousness, severity, and causality to the study drug. A detailed narrative summarizing

*CONFIDENTIAL*

the course of the event, including its evaluation, treatment, and outcome must be provided. Specific or estimated dates of event onset, treatment, and resolution must be included when available. Medical history, concomitant medications, and laboratory data that are relevant to the event will also be summarized in the narrative. For fatal events, the narrative will state whether an autopsy was or will be performed and include the results if available. Source documents (including medical reports) will be retained at the study site and must not be submitted to the Sponsor for SAE reporting purposes.

Grade 3 or Grade 4 AEs ongoing at the discontinuation of the study drug will be monitored (including local laboratory tests when appropriate, see Section 3.3) until the AE is determined to be resolving or back to baseline.

Additional relevant information regarding the AESIs ILD/pneumonitis (Section 11.11), regardless of seriousness, is to be collected through the targeted questionnaires within the eCRF. Additional relevant information regarding the AESI infusion-related reaction (Section 11.11) is to be collected through the narrative form within the eCRF.

For broad surveillance of ILD/pneumonitis, a set of pre-defined list of preferred terms eligible for adjudication as described in the Event Adjudication Site Manual, is utilized for enhanced data collection.

Disease progression/worsening of the cancer will not be recorded as an AE on the Adverse Event eCRF. However, events associated with disease progression, such as clinical symptoms, may be recorded as AEs. Death due to disease progression should be recorded on the Death eCRF.

If the AE is serious, it must be reported immediately to Innovations Safety Department via electronic data capture (EDC). Other untoward events occurring in the framework of a clinical study are to be recorded as AEs (i.e., AEs that occur prior to assignment of study treatment that are related to a protocol-mandated intervention, including invasive procedures such as biopsies, medication washout, or no treatment run-in).

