Any clinically significant signs and symptoms, abnormal test findings, changes in physical examination, hypersensitivity, and other measurements that occur will be reported as AEs, and reported on the relevant eCRF screen.

Test findings will be reported as an AE if the test result requires an adjustment in the study drug(s) or discontinuation of treatment; and/or test findings require additional testing or surgical intervention; a test result or finding is associated with accompanying symptoms; or a test result is considered to be an AE by the Investigator.

All AEs should be recorded individually in the patient's own words (verbatim) unless, in the opinion of the Principal Investigator or designated physician, the AEs constitute components of a recognized condition, disease, or syndrome. In the latter case, the condition, disease, or syndrome should be named rather than each individual sign or symptom. If a constellation of signs and/or symptoms cannot be medically characterized as a single diagnosis or syndrome at the time of reporting, each individual event should be recorded as an AE or SAE as appropriate on the relevant form(s) (eCRF screen). If a diagnosis is subsequently established, it must be

*CONFIDENTIAL*

reported as follow-up information is available. If a diagnosis is determined subsequent to the reporting of the constellation of symptoms, the signs/symptoms should be updated to reflect the diagnosis.

A persistent AE is one that extends continuously, without resolution, between patient evaluation time points. All persistent AEs that meet the SAE criteria must be recorded on the eCRF.

A recurrent AE is one that occurs and resolves between patient evaluation time points and subsequently recurs. All recurrent AEs that meet the SAE criteria must be recorded on the eCRF.

Infusion-related reactions should be recorded and reported under the AE term “Infusion related reaction.” All applicable symptoms or signs of IRR (e.g. flushing, tachycardia, nausea, and bronchospasm) can be described in the narrative form on the eCRF.

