### **11.2.2 Reporting of Adverse Events**

All AEs regardless of seriousness or relationship to DS-6157a treatment (called study treatment), spanning from the signing of the ICF until 30 calendar days after discontinuation or completion of study treatment as defined by the study for that patient after his/her last dose of study drug, are to be recorded on the corresponding screen(s) included in the eCRF.

All AEs resulting in discontinuation from the study should be followed until resolution or stabilization. All new AEs occurring during this period must be reported and followed until resolution unless, in the opinion of the Investigator, the AE or laboratory abnormality/ies is/are not likely to improve because of the underlying disease. In this case, the Investigator must record his or her reasoning for this decision in the patient’s medical record.

After 30 days after completion of protocol-specific treatment or discontinuation, only AEs, SAEs, or deaths assessed by the Investigator as treatment-related are to be reported.

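### Section 11.8 bars reporting symptoms of metastasis as AEs while Section 11.2.1 lets them be recorded, so a misattributed symptom can drop out of the TEAE, SAE and DLT data unreviewed

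*Combined protocol and SAP*

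**What the plan says.** Several current passages of the protocol bear on a clinical symptom that the investigator links to metastatic disease.

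- Section 11.8, which separates new primary cancers from metastases, states: "Symptoms of metastasis or the metastasis itself should not be reported as an AE/SAE, as they are considered to be disease progression".
- Section 11.2.1 keeps progression itself off the AE form but adds that "events associated with disease progression, such as clinical symptoms, may be recorded as AEs". Further on it gives a general rule: "Any clinically significant signs and symptoms, abnormal test findings, changes in physical examination, hypersensitivity, and other measurements that occur will be reported as AEs".
- Sections 7.1 and 11.2.2 are general collection rules. They cover "All AEs regardless of seriousness or relationship to DS-6157a treatment" and do not mention progression or metastasis.
- Section 11.1.1 defines an AE without any causal judgement. Section 11.3 assigns an AE reasonably explained by the disease under study to the unrelated category.
- Section 10.5.3.1 builds TEAEs from reported AEs with onset on treatment. Section 5.1.2 defines a DLT as a TEAE, "excluding toxicities clearly related to disease progression or intercurrent illness".
- Section 11.6 has disease progression entered as an AE term, and expedited, when a patient dies of it with no other immediate cause. Section 11.2.1 says progression is not an AE and sends such deaths to the Death eCRF.

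**The concern.** Under 11.8 the investigator's attribution decides whether an event exists in the database at all. Everywhere else the order is reversed: the event is recorded, its causality is assessed, and for DLTs it is then judged whether the link to progression is clear. Two sites following different sections would handle the same symptom differently.

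This matters because all patients have unresectable and/or metastatic GIST. Section 1.2 lists nausea and vomiting as identified risks, and diarrhea and colitis as potential ones. That such symptoms may resemble those of abdominal disease is my assumption, but a plausible one. No untreated arm shows a background rate. Section 10.9 forgoes a Data Monitoring Committee and relies in part on individual AE reports and their aggregates. Because 11.8 only removes events, any error it causes lowers the counts.

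**Working it through.** **Step 1. The rules side by side, for a symptom attributed to metastasis.**

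| Section | Rule | Names these symptoms? |
|---|---|---|
| 11.8 | Not reported as AE/SAE | Yes |
| 11.2.1, progression sentence | Recording permitted | Yes, as progression-associated symptoms |
| 11.2.1, general sentence | Reported if clinically significant | No |
| 7.1 and 11.2.2 | All AEs recorded, whatever the relationship | No |
| 11.3 | Disease-explained AE is classed as unrelated | Disease under study is named |

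The direct conflict is prohibition (11.8) against permission (11.2.1). The general rules add weight, and neither they nor the permissive sentence refers to 11.8.

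**Step 2. The data path.** An event withheld under 11.8 is not a reported AE, so it is neither a TEAE (10.5.3.1) nor a DLT (5.1.2). If the patient received the full Cycle 1 dose and completed the window, he or she still belongs to the DLT-Evaluable Set, now as a patient without a DLT. One DLT in three is then read as 0/3.

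**Step 3. Which events have another route.** Scheduled laboratory results are summarised, with Grade 3 or higher results listed (10.5.3.2). Potential Hy's Law cases are reported within 24 hours whether or not the investigator considers them AEs (11.4). Dose interruptions and modifications go on the AE and drug administration forms (Section 6). What remains exposed is mainly symptomatic events that trigger none of these.

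**Step 4. Sensitivity of the dose model to one missing DLT.** Inputs from Section 10.7:

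- Model: logit π(d) = ln α + β ln(d/9.6).
- Prior: ln α with mean −1.125 and SD 1.373; ln β with mean −0.308 and SD 0.778; correlation 0.
- Rule: among doses with P(π > 33%) < 25% and an increment of at most 100%, take the one with the highest posterior probability of (16%, 33%].

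The posterior was integrated on an 801 × 801 grid. Of 15 Table 3.1 rows checked, 13 reproduce. Rows 1.6 and 1.19 differ because P(π > 33%) at the deciding dose is 0.247 and 0.251, on the 0.25 limit and within simulation error. All six rows used below reproduce.

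| Dose just tested (mg/kg; lower doses 0/3) | Next dose at 1/3 | Next dose at 0/3 | P(π > 33%) at tested dose, 1/3 → 0/3 | Table 3.1 rows |
|---|---|---|---|---|
| 1.6 | 1.6 | 3.2 | 0.213 → 0.024 | 2.1, 1.1 |
| 3.2 | 4.8 | 6.4 | 0.115 → 0.015 | 1.13, 1.2 |
| 6.4 | 8.0 | 9.6 | 0.123 → 0.021 | 1.4, 1.3 |

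These figures show what one lost DLT does to the model. They say nothing about how often one would be lost.

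**The case against.** The best defence is that 11.8 is a specific exception to general rules. It sits under new cancers and gives its reason: metastasis counts as progression. Sections 7.1 and 11.2.2 and the general sentence of 11.2.1 do not name these symptoms. A reader might infer that they expressly demand them, but the documents do not go that far. The defence fails against the other sentence of 11.2.1, which is just as specific and points the opposite way, and it sits badly with 11.3.

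Other parts of the defence stand and limit the point:

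- A reader might infer that any unrecorded Grade 3 event shifts the dose. Table 3.1 counts DLTs. Section 5.1.2 exempts Grade 3 nausea, vomiting, diarrhea or anorexia that improves to Grade 2 or lower within 3 days under maximal management, and Grade 3 anemia counts only if transfusion is required.
- Section 5.1.2 already removes toxicities clearly related to progression, so for DLTs 11.8 adds only the unclear or wrongly attributed ones.
- A reader might infer that the safety team would be blind to anemia and hepatic toxicity. The routes in Step 3 contradict that.
- Eligibility is unresectable and/or metastatic disease, so not every patient has metastases. Section 11.7 also has a pre-existing condition recorded when it worsens, although for a baseline symptom of metastasis that again conflicts with 11.8.
- The chosen dose is not set by the model alone. Appendix G and 5.1.1 also weigh clinical safety and other data.

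**Conclusion.** The inconsistency is real and lies wholly in current text. Followed as written, 11.8 lets an investigator keep a symptomatic event out of the TEAE, SAE and DLT data by attributing it to metastasis, with no threshold comparable to 5.1.2 and nothing left to review. The likely loss is confined mainly to misattributed symptomatic events such as nausea, vomiting and other gastrointestinal complaints.

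Its size cannot be estimated, because the documents give no rate of misattribution. The dose shifts (1.6 to 3.2, 4.8 to 6.4, 8.0 to 9.6 mg/kg) are conditional on the missed event meeting the DLT definition in a cohort of three, with the patient counted as evaluable and the model recommendation followed. They should not be read as expected bias. The text should be corrected because the exposure is one-directional, cohorts are small and the remedy is cheap.

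**What to change.** Reconcile 11.2.1, 11.6 and 11.8 into one recording rule:

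1. In 11.8, strike the reference to symptoms, so that only the metastasis itself is not an AE.
2. In 11.2.1, replace the permissive wording with a statement that clinical symptoms are recorded as AEs with causality assessed, including those thought to come from progression. Attribution to progression is then judged on recorded events under 5.1.2.
3. Align 11.6 with 11.2.1 on whether progression is entered as an AE term when a patient dies of it, and on which form carries the death.

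The DLT criteria and patient care do not change. The cost is a few wording edits, a note in the eCRF guidance and somewhat more disease-related AE entries, which the causality field would identify.

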### **11.9 Pregnancy, Abortion, Birth Defects/Congenital Anomalies**

If a patient becomes pregnant while enrolled in the study, EIU Reporting Form (a paper report form, not available within the eCRF) must be completed and Faxed [contact])/Emailed ([[contact]](mailto:[contact])) to the Innovations Safety Department. The Innovations Safety Department should be notified expeditiously, irrespective of whether or not it meets the criteria for expedited reporting. Abortions (spontaneous, accidental, or therapeutic) must also be reported to the Innovations Safety Department.

If a female partner of a male patient becomes pregnant during the male patient's participation in this study, this must be reported to the Innovations Safety Department immediately. Every effort should be made to follow the pregnancy for the final pregnancy outcome.

Congenital anomalies/birth defects always meet SAE criteria, and should therefore be expeditiously reported as an SAE, using the previously described process for SAE reporting. An EIU Report Form should also have been previously completed, and will need to be updated to reflect the outcome of the pregnancy.

